## 10.11. Appendix 11: Protocol Amendment History

### Amendment 1 (23 Jun 2022)

**Overall Rationale for the Amendment:** To update from BID to QD dosing schedule; clearly delineate PK sample collection schemas for Cohort 1 and for Cohort 2 when HD is given on specific days; clarify that the Tasso device is the preferred method of PK sampling; and clarify eDiary data collection and other study procedures.

Section # and Name	Description of Change	Brief Rationale	Substantial or Nonsubstantial
1. Protocol Summary 4. Study Design 6. Study Intervention(s) and Concomitant Therapy	Nirmatrelvir/ritonavir 100 mg /100 mg Q12 hr dose on Days 1-5 changed to a single dose on Day 1 of PF-07321332 (nirmatrelvir)/ritonavir 300 mg/100 mg followed by PF-07321332 (nirmatrelvir)/ritonavir 150 mg/100 mg QD on Days 2-5.	Considering the uncertainty in safety in this vulnerable population, higher exposure with BID dosing regimen is concerning. Population PK model-based simulations showed that 300 mg PF-07321332 (nirmatrelvir) on Day 1 and 150 mg of PF-07321332 (nirmatrelvir) QD on Day 2 to Day 5 with 100 mg ritonavir gives comparable exposure to COVID-19 patients with normal renal function at the 300 mg PF-07321332 (nirmatrelvir)/100 mg ritonavir BID dose for 5 days.	Substantial (impacts scientific value/conduct/management of the trial).
1.2 Schema	Revised for QD dosing.	Revised for QD dosing.	Substantial (impacts scientific value/conduct/management of the trial).
1.3 SoA 6. Study Intervention(s) and Concomitant Therapy	Revised dosing windows to allow for Day 1-Day 2 to be no earlier than 14 hours and no later than 28 hours after the Day 1	Revised for QD dosing.	Substantial (impacts scientific value/conduct/management of the trial).

Section # and Name	Description of Change	Brief Rationale	Substantial or Nonsubstantial
	dose and for the remaining doses (Days 3-5) to be taken at approximately the same time ( $\pm 4$ hours) as the Day 2 dose.		
1.3 PK Sampling Schemas	Additional PK sampling tables were added for Cohort 2.	Tables were added to for both cohorts to show the different PK collection scenarios as related to dosing and HD.	Substantial (impacts scientific value/conduct/management of the trial).
8.4. AEs, SAEs, and Other Safety Reporting 10.3. Adverse Events: Definitions and Procedures for Recording, Evaluating, Follow Up, and Reporting	Revised CT SAE Report Form to PSSA.	This study will use the PSSA tool for reporting SAEs.	Nonsubstantial
1. Inclusion Criteria 5. Study Population 10.4.1 Male Participant Reproductive Inclusion Criteria	Inclusion criterion 1 revised: deletion of requirement for male contraception.	Exposure to females through seminal fluid will be sufficiently low and therefore precludes the need for male contraception.	Nonsubstantial
1.1. Synopsis 5. Study population	Exclusion criterion 3 revised.	Simplification of chronic liver disease criteria. This update includes removal of need for INR testing at screening.	Nonsubstantial
1.1. Synopsis 5. Study population	Exclusion criterion 4 revised.	HIV medications are not prohibited but will be reviewed during concomitant medication review per	Nonsubstantial

Section # and Name	Description of Change	Brief Rationale	Substantial or Nonsubstantial
		Screening procedures and Appendix 8.	
6.5. Study Intervention Compliance	Updated definitions of medication errors.	Revised for QD dosing.	Nonsubstantial
1.3. Schedule of Activities	Added maximum time between dosing of the two study interventions as 15 minutes.	To allow additional time between taking the study interventions.	Nonsubstantial
1.3 SoA 8.1.1. Tasso Sample Training and Collection	Tasso device instruction.	Clarification that use of Tasso device is the preferred method of PK sampling. If Tasso device is not available or unable to function properly, only then is a venous draw permitted.	Nonsubstantial
8.1.4. Home Health Visits	Addition of the procedure to review and record COVID-19 related hospitalizations.	Correction of an important end point omission.	Nonsubstantial
1.3 SoA 8.5.4 Electronic diary	Clarification of eDiary use and addition of investigative site compliance check.	Clarification of eDiary use and requirement of compliance check by the investigative site.	Nonsubstantial
CCI			
9.5. Sample Size Determination	Added that participants may be prelaced.	To ensure sufficient PK data for analysis, any participant with insufficient PK samples for analysis may be replaced.	Nonsubstantial
1. Protocol Title, Rationale, Inclusion Criteria	Minor word changes, administrative.	Clarification.	Nonsubstantial

Section # and Name	Description of Change	Brief Rationale	Substantial or Nonsubstantial
8.7 Biomarkers Table 4, Appendix 10			
Throughout the protocol	Electronic diary will not be used to collect PK sample times.	PK collection times will be captured on the sample requisition forms that are submitted to the laboratories.	Nonsubstantial
Throughout the protocol	Changed “nirmatrelvir” to “PF-07321332 (nirmatrelvir)”.	To be consistent with study drug bottle labeling.	Nonsubstantial

## 10.12. Appendix 12: Abbreviations

The following is a list of abbreviations that may be used in the protocol.

Abbreviation	Term
Abs	absolute
ADL	activity/activities of daily living
AE	adverse event
AKI	acute kidney injury
ALT	alanine aminotransferase
ARDS	acute respiratory distress syndrome
AST	aspartate aminotransferase
AUC	area under the plasma concentration-time curve
AUC 0-tau	AUC over a dosing interval
AUC inf	AUC from time 0 extrapolated to infinite time
AxMP	auxiliary medicinal product
BID	twice daily
BP	blood pressure
CDC	Centers for Disease Control and Prevention
CFR	Code of Federal Regulations
CI	confidence interval
CIOMS	Council for International Organizations of Medical Sciences
CK	creatinine kinase
CKD	chronic kidney disease
CKD-EPI	chronic kidney disease epidemiology
CL/F	apparent oral clearance
CLd	hemodialysis clearance
C max	maximum plasma concentration
C min	minimum plasma concentration
CO 2	carbon dioxide (bicarbonate)
CONSORT	Consolidated Standards of Reporting Trials
COVID-19	coronavirus disease 2019
CRF	case report form
CRO	contract research organization
CSR	Clinical Study Report
CT	computed tomography/clinical trial
CTIS	Clinical Trial Information System
C trough	Pre-dose trough concentration
CV	coefficient of variation
CYP	cytochrome P450
DAIDS	Division of AIDS
DCT	data collection tool
DDI	drug-drug interaction
DICI	drug-induced creatinine increase
DIKI	drug-induced kidney injury

Abbreviation	Term
DILI	drug-induced liver injury
DU	dispensable unit
EC	ethics committee
EC90	90% effective concentration
ECC	emergency contact card
ECDC	European Centre for Disease Prevention and Control
ECG	electrocardiogram or electrocardiography
eCrCl	estimated creatinine clearance
eCRF	electronic case report form
EDB	exposure during breastfeeding
eDiary	electronic diary
E-DMC	External Data Monitoring Committee
EDP	exposure during pregnancy
eGFR	estimated glomerular filtration rate
ET	early termination
EU	European Union
EUA	Emergency Use Authorization
EudraCT	European Union Drug Regulating Authorities Clinical Trials (European Clinical Trials Database)
Fd	fraction of drug removed from the body
FDA	Food and Drug Administration
GCP	Good Clinical Practice
GGT	gamma-glutamyl transferase
HA	health authority
HCP	healthcare provider
HCV	hepatitis C virus
HD	hemodialysis
HIV	human immunodeficiency virus
HMG-CoA	3-hydroxy-3-methylglutaryl coenzyme A
HRT	hormone replacement therapy
IB	Investigator's Brochure
ICD	informed consent document
ICH	International Council for Harmonisation of Technical Requirements for Pharmaceuticals for Human Use
ID	identification
IgG	immunoglobulin G
IgM	immunoglobulin M
IMP	investigational medicinal product
IND	Investigational New Drug
INR	international normalized ratio
IP	investigational product
IPAL	Investigational Product Accountability Log
IPM	investigational product manual

Abbreviation	Term
IRB	Institutional Review Board
IRT	Interactive Response Technology
IUD	intrauterine device
IV	intravenous
KDIGO	Kidney Disease: Improving Global Outcomes
LFT	liver function test
mAb	monoclonal antibody
M pro	main protease
MQI	medically qualified individual
N	number of
NA	not applicable
NAAT	nucleic acid amplification test
NHP	non-human primates
NIH	National Institutes of Health
NIMP	non-investigational medicinal product
NOAEL	no adverse event observed level
NP	nasopharyngeal
PaO  /FiO 	ratio of arterial partial pressure of oxygen to fraction of inspired oxygen
PDE5	phosphodiesterase type 5
PE	physical examination
PK	pharmacokinetic(s)
PopCL	population clearance
PR	pulse rate
PSSA	Pfizer's Serious Adverse Event Submission Assistant
PT	prothrombin time
QD	daily
RBC	red blood cell
RNA	ribonucleic acid
RT-PCR	reverse transcription–polymerase chain reaction
SAE	serious adverse event
SAP	Statistical Analysis Plan
SARS-CoV-2	severe acute respiratory syndrome coronavirus 2
SAS	safety analysis set
Scr	serum creatinine
Scys	serum cystatin C
SD	standard deviation
SoA	schedule of activities
SoC	standard of care
SOP	standard operating procedure
SpO 	oxygen saturation
SRSD	Single Reference Safety Document
SUSAR	Suspected Unexpected Serious Adverse Reaction

Abbreviation	Term
T bili	total bilirubin
$t_{1/2}$	terminal half-life
TB	tuberculosis
TEAE	treatment-emergent adverse event
$T_{max}$	maximum plasma concentration
UACR	urine albumin/creatinine ratio
UADE	unanticipated adverse device effect
ULN	upper limit of normal
US	United States
Vz/F	apparent volume of distribution
WBC	white blood cell
WHO	World Health Organization
WOCBP	woman/women of childbearing potential
$\beta$ -hCG	$\beta$ -human chorionic gonadotropin

1. VERSION HISTORY

Table 1. Summary of Changes			
Version/ Date	Associated Protocol Amendme nt	Rationale	Specific Changes
1.0	1.0		SAP original version

For the entire document, text in *Italic* format will represent language copied directly from protocol.

2. INTRODUCTION

The purpose of this study is to evaluate the safety and PK of PF-07321332 (nirmatrelvir)/ritonavir in adults with severe renal impairment and COVID-19. Eligible participants include those with severe renal impairment (defined as eGFR <30 mL/min/1.73 m²) and not yet receiving HD (Cohort 1) and individuals receiving HD (Cohort 2).

2.1. Modifications to the Analysis Plan Described in the Protocol

Not applicable.

2.2. Study Objectives, Endpoints, and Estimands

Table 2. Objectives and Endpoints

Objectives	Endpoints	Estimands
Primary:	Primary:	Primary:

To describe the safety and tolerability of nirmatrelvir/ritonavir in adult participants with COVID-19 and severe renal impairment.	
Incidence of TEAEs.Incidence of SAEs and AEs leading to discontinuations.	
Not Applicable.
Secondary:	Secondary:	Secondary:

To evaluate the effect of severe renal impairment on the PK of nirmatrelvir in participants not on HD.To evaluate the effect of severe renal impairment on the PK of nirmatrelvir in participants on HD.	
Plasma nirmatrelvir PK parameters including C_{max}, CL/F, Vz/F, AUC_{0-tau}, t_{1/2}, and C_{trough} estimated from the population PK model.	
Not Applicable.
CC1	
HD clearance (CL_d) of nirmatrelvir.Fraction of nirmatrelvir dose removed from the body by dialysis (F_d)	
Not Applicable.

CCI

2.2.1. Primary Estimand(s)

Not applicable.

2.2.2. Secondary Estimand(s)

Not applicable.

2.2.3. Additional Estimand(s)

[figure not shown]
Not applicable.

2.3. Study Design

This is a Phase 1, open-label study to evaluate the effect of severe renal impairment on the PK of nirmatrelvir/ritonavir and the safety and tolerability of nirmatrelvir/ritonavir in adult participants with COVID-19 and severe renal impairment and not yet receiving intermittent hemodialysis (Cohort 1) and severe renal impairment receiving intermittent hemodialysis (Cohort 2). The study will be conducted in 2 parallel cohorts. Cohort 1 will enroll eligible participants with severe renal impairment (defined as eGFR <30 mL/min/1.73 m²) not on hemodialysis. Cohort 2 will enroll eligible participants with severe renal impairment on hemodialysis. All eligible participants will be assigned to receive a single dose of PF-07321332 (nirmatrelvir)/ritonavir 300 mg/100 mg orally on Day 1 followed by PF-07321332 (nirmatrelvir)/ritonavir 150 mg/100 mg QD from Day 2 to Day 5.

Approximately 24 participants (12 participants in Cohort 1 and 12 participants in Cohort 2) will be assigned to study intervention.

Figure 1. Study Design

- Screening and baseline visits may be a combination of in-person and telemedicine visits. Screening period is 1-2 days and participants can be screened and randomized on the same day but must be randomized by the second day (Day 1 of study intervention).
- The Baseline/Day 1 visit must be in person at the site.
- In-person visits at Days 14 and 34 are required only if procedures per SoA need to be performed or if clinically relevant abnormal laboratory values were present from a sample drawn at the previous study visit and need to be repeated.

2.4. Sample Size Determination

The 12 evaluable participants per cohort is considered sufficient to provide a suitable estimate of precision of PK parameters of nirmatrelvir in severe renal impairment participants on HD and not on HD, in which provides approximately 40% precision (the width of 90% confidence interval) for AUC_{inf} and C_{max} . To ensure sufficient PK data for analysis, any participant with insufficient PK samples for analysis may be replaced.

To identify an adequate sample size for PK, we assessed the precision of estimating the PK parameter using different sample sizes, as defined by the width of the resultant confidence intervals represented as a percentage of the mean value of the PK parameter. Currently, no PK data is available in severe renal impairment following multiple doses of nirmatrelvir; therefore, a single dose PK data of nirmatrelvir in severe renal impairment adults not on dialysis (Table 3) was used to determine the CV estimates for nirmatrelvir PK parameters. The CV estimates in Table 3, for nirmatrelvir AUC_{inf} and C_{max} range from 33% to 38% (ie, 0.33 to 0.38).

Table 3. PF-07321332 (nirmatrelvir) PK Parameters Following Single Dose of PF-07321332 (nirmatrelvir) /Ritonavir 100 mg/100 mg in Severe Renal Impairment Patients

PK Parameter (units)	Nirmatrelvir (N=8)
C_{max} (ng/mL)	2369 (38)
AUC_{inf} (ng*hr/mL)	44040 (33)
T_{max} (hr)	3.00 (1.00-6.05)
$t_{1/2}$ (hr)	13.37 ± 3.3225

Values are presented as geometric mean (geometric % CV) except median (range) for T_{max} and arithmetic mean ± SD for $t_{1/2}$.

The study participants may experience more variability in PK parameters than the available data given the wider range of multiple doses, thus a precision is described with an anticipated CV of 0.2, 0.3, or 0.4.

Table 4 below shows the upper and lower confidence limits and 90% CI width for the mean PK parameter (eg, AUC , $t_{1/2}$, or C_{max}), presented as a percentage of the mean, for different N and CV. With a sample size of 12 evaluable participants and a CV equal to 0.4, the 90% CI will range from 79.3% – 120.7 % of the mean, and the corresponding CI width will be 41.4% of the mean. The PK parameter will be estimated with a tight 95% CI in the a severe renal impaired population.

Table 4. Percentile Range and Width of 90% Confidence Intervals for the Mean PK Parameter

N	CV=0.2		CV=0.3		CV=0.4	
	Range	Width	Range	Width	Range	Width
8	86.6-113.4%	26.8%	79.9-120.1%	40.2%	73.2-126.8%	53.6%
10	88.5-111.5%	23.1%	82.7-117.3%	34.6%	76.9-123.1%	46.2%
12	89.6-110.4%	20.7%	84.5-115.5%	31.1%	79.3-120.7%	41.4%
14	90.5-109.5%	19.0%	85.8-114.2%	28.4%	81.1 -119.0%	37.9%

3. ENDPOINTS AND BASELINE VARIABLES: DEFINITIONS AND CONVENTIONS

3.1. Primary Endpoint

- Incidence of TEAEs
- Incidence of SAEs and AEs leading to discontinuations.

3.2. Secondary Endpoint(s)

- Plasma PF-07321332 (nirmatrelvir) PK parameters including C_{max} , CL/F, Vz/F,

$AUC_{0-\tau}$, $t_{1/2}$, and C_{trough} estimated from the population PK model.

- HD clearance (CL_d) of PF-07321332 (nirmatrelvir).
- Fraction of PF-07321332 (nirmatrelvir) dose removed from the body by dialysis (F_d).

CCI

3.4. Baseline Variables

Baseline visit is set up according to study days of Day -1 to Day 1. Only non-missing results that are prior to the first dose intervention will be considered as Baseline data. The variables for baseline include vital signs, labs (hematology, chemistry, and additional tests), COVID-19 vaccination status, SARS-CoV-2 serology, SARS-CoV-2 RNA, and prior medications. For SARS-CoV-2 RNA concentration data, the Baseline data is on Day 1.

3.5. Safety Endpoints

The safety endpoints of this study are:

- Incidence of TEAEs.
- Incidence of SAEs and AEs leading to discontinuations.

Clinical Data Interchange Standards Consortium (CDISC) and Pfizer Standards (CaPS) will be used for the analysis of standard safety data.

3.5.1. Adverse Events

An adverse event (AE) is any untoward medical occurrence in a study participant administered a product or medical device; the event need not necessarily have a causal relationship with the treatment or usage. An adverse event is considered a Treatment-

Emergent Adverse Event (TEAE) if the event started on or after the study medication start date and time.

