### **Number of Participants:**

Approximately 24 participants (12 participants in Cohort 1 and 12 participants in Cohort 2) will be assigned to study intervention.

Note: "Enrolled" means a participant's, or their legally authorized representative's, agreement to participate in a clinical study following completion of the informed consent process and assignment to study intervention. A participant will be considered enrolled if the informed consent is not withdrawn prior to participating in any study activity. Potential participants who are screened for the purpose of determining eligibility for the study, but do not participate in the study, are not considered enrolled.

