**Study Arms and Duration:**

Eligible participants will receive a single dose of PF-07321332 (nirmatrelvir)/ritonavir 300 mg/100 mg orally on Day 1 followed by PF-07321332 (nirmatrelvir)/ritonavir 150 mg/100 mg QD from Day 2 to Day 5. The total study duration is up to 38 days and includes a 1-to-2-day screening period where participants can be screened on one day and randomized the next day or screened and randomized on the same day. Screening procedures can be performed over 2 days, but the participant must be randomized by the second day (Day 1) and begin study treatment. Therefore, Screening and Randomization can take no longer than 2 consecutive days. After Screening, the participant takes study intervention for 5 days and completes the safety follow-up period through Day 34. This equates to a total study duration of up to 38 days.

Study Intervention(s)	
Intervention Name	PF-07321332 (nirmatrelvir)/ritonavir
Arm Name (group of participants receiving a specific treatment or no treatment)	All participants will receive the same treatment open-label
Unit Dose Strength(s)	PF-07321332 (nirmatrelvir) 150 mg Ritonavir 100 mg
Route of Administration	Oral
Use	Experimental
IMP or NIMP/AxMP	IMP

Study Arm(s)	
Arm Title	PF-07321332 (nirmatrelvir)/ritonavir (5-Days)
Arm Type	Experimental
Arm Description	Participants will receive PF-07321332/ritonavir 300 mg/100 mg on Day 1 followed by PF-07321332/ritonavir 150 mg/100 mg QD from Day 2 to Day 5.

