#### **8.4.1. Time Period and Frequency for Collecting AE and SAE Information**

The time period for actively eliciting and collecting AEs and SAEs (“active collection period”) for each participant begins from the time the participant provides informed consent, which is obtained before undergoing any study-related procedure and/or receiving study intervention, through and including a minimum of 28 calendar days, except as indicated below, after the last administration of the study intervention.

Follow-up by the investigator continues throughout the active collection period and until the AE or SAE or its sequelae resolve or stabilize at a level acceptable to the investigator.

When a clinically important AE remains ongoing at the end of the active collection period, follow-up by the investigator continues until the AE or SAE or its sequelae resolve or stabilize at a level acceptable to the investigator and Pfizer concurs with that assessment.

For participants who are screen failures, the active collection period ends when screen failure status is determined.

If the participant withdraws from the study and also withdraws consent for the collection of future information, the active collection period ends when consent is withdrawn.

If a participant permanently discontinues or temporarily discontinues study intervention because of an AE or SAE, the AE or SAE must be recorded on the CRF and the SAE reported using the PSSA.

Investigators are not obligated to actively seek information on AEs or SAEs after the participant has concluded study participation. However, if the investigator learns of any SAE, including a death, at any time after a participant has completed the study, and they consider the event to be reasonably related to the study intervention, the investigator must promptly report the SAE to Pfizer using the PSSA.

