## **10.3. Appendix 3: Adverse Events: Definitions and Procedures for Recording, Evaluating, Follow-Up, and Reporting**

### **10.3.1. Definition of AE**

AE Definition

• An AE is any untoward medical occurrence in a patient or clinical study participant, temporally associated with the use of study intervention, whether or not considered related to the study intervention.

• Note: An AE can therefore be any unfavorable and unintended sign (including an abnormal laboratory finding), symptom, or disease (new or exacerbated) temporally associated with the use of study intervention.

Events Meeting the AE Definition

• Any abnormal laboratory test results (hematology, clinical chemistry, or urinalysis) or other safety assessments (eg, ECG, radiological scans, vital sign measurements), including those that worsen from baseline, considered clinically significant in the medical and scientific judgment of the investigator. Any abnormal laboratory test results that meet any of the conditions below must be recorded as an AE:

• Is associated with accompanying symptoms.

• Requires additional diagnostic testing or medical/surgical intervention.

• Leads to a change in study dosing (outside of any protocol-specified dose adjustments) or discontinuation from the study, significant additional concomitant drug treatment, or other therapy.

• Exacerbation of a chronic or intermittent preexisting condition, including an increase in either frequency and/or intensity of the condition.

• New condition detected or diagnosed after study intervention administration, even though it may have been present before the start of the study.

• Signs, symptoms, or the clinical sequelae of a suspected drug-drug interaction.

• Signs, symptoms, or the clinical sequelae of a suspected overdose of either study intervention or a concomitant medication. Overdose per se will not be reported as an AE or SAE unless it is an intentional overdose taken with possible suicidal/self-harming intent. Such overdoses should be reported regardless of sequelae.

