#### Follow-Up of AEs and SAEs

- The investigator is obligated to perform or arrange for the conduct of supplemental measurements and/or evaluations, as medically indicated or as requested by the sponsor, to elucidate the nature and/or causality of the AE or SAE as fully as possible. This may include additional laboratory tests or investigations, histopathological examinations, or consultation with other healthcare providers.
- If a participant dies during participation in the study or during a recognized follow-up period, the investigator will provide Pfizer Safety with a copy of any postmortem findings, including histopathology.
- New or updated information will be recorded in the originally submitted documents.
- The investigator will submit any updated SAE data to the sponsor within 24 hours of receipt of the information.

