6. ANALYSES AND SUMMARIES

6.1. Primary Endpoint

6.1.1. Primary Endpoint/Estimand Analysis

6.1.1.1. Main Analysis

Incidence of TEAEs through Day 34, SAEs, and AEs leading to discontinuation will be summarized with number and percent of participants in the SAS for each cohort, and overall, in accordance with CDISC and CaPS standards.

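### The SAP defines a TEAE by onset alone, so a non-serious AE recorded before first dose that worsens on treatment can be left out of the TEAE count

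*SAP*

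**What the plan says.** SAP 3.5.1 counts an AE as treatment-emergent "if the event started on or after the study medication start date and time". The protocol lists the abbreviation TEAE but does not define the term.

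Protocol 8.4.1 says that the active collection period "begins from the time the participant provides informed consent", and the Schedule of Activities marks AE monitoring at Screening. The interval before dosing is short: "Screening and Randomization can take no longer than 2 consecutive days" (Protocol 1.1, Study Arms and Duration).

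Protocol 10.3.1 lists among events that meet the AE definition: "Exacerbation of a chronic or intermittent preexisting condition, including an increase in either frequency and/or intensity of the condition". Protocol Appendix 3, under follow-up of AEs and SAEs, says: "New or updated information will be recorded in the originally submitted documents". Under assessment of intensity, the same appendix has the investigator assign each event to one grade.

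The primary endpoint has two parts, TEAE incidence and "Incidence of SAEs and AEs leading to discontinuations" (SAP 3.1). The analysis reads: "Incidence of TEAEs through Day 34, SAEs, and AEs leading to discontinuation will be summarized with number and percent of participants in the SAS" (SAP 6.1.1.1), by cohort and overall.

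**The concern.** AE collection starts before dosing, but the TEAE rule looks only at when the event began. An AE entered between consent and first dose, updated in place when it becomes more severe on treatment, keeps its pre-dose start date and fails the SAP test.

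TEAE incidence is the first-listed primary endpoint, and worsening of an existing complaint is a plausible form of drug effect in this population. Nausea, vomiting and diarrhea appear both among the ritonavir risks (Protocol 2.3.1) and among COVID-19 symptoms (Protocol Appendix 10). Protocol 5.3.2.1 adds that nausea and vomiting are common in severe CKD and can be made worse by dialysis. Cohort 2 participants who start on a dialysis day take the first dose after dialysis; six of the eleven Cohort 2 sampling schemas (2 to 7) have this start. An event that begins during dialysis and worsens after the first dose is therefore foreseeable.

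Two sites could also record the same clinical course differently, and only one of the two records would count. Compared with a definition that includes worsening, the onset-only rule can only lower the reported incidence.

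**Working it through.** The plan states no figure on this point, so the check is to follow one case through the rules and then to scale it.

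**The case.** A participant consents, has an AE recorded before first dose, and the AE becomes more severe after first dose.

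1. *Worsening entered as a new AE.* Protocol 10.3.1 allows this, because an exacerbation is itself an AE. The onset is post-dose, so SAP 3.5.1 counts it as a TEAE.
2. *Original record updated.* The follow-up text in Protocol Appendix 3 points this way. The onset stays pre-dose, so SAP 3.5.1 does not count it as a TEAE.
3. *Event becomes serious or leads to discontinuation.* The second primary component counts it under either way of recording, because that component is not worded as restricted to treatment-emergent events.
4. *Symptom is an expected part of COVID-19 at entry.* Protocol 10.3.1 does not treat it as an AE unless it is more severe than expected. If it first exceeds expectation after dosing, it first qualifies as an AE then. Entered with that onset, it is a TEAE.

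Only branch 2 loses the event. Neither document says whether branch 1 or branch 2 applies.

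**Conditions for a participant to be missed.** All of these must hold: the event arises after consent and before first dose (at most 2 consecutive days); it qualifies as an AE; it worsens after dosing; it stays on one record; it is not serious and does not lead to discontinuation; and the participant has no other TEAE.

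**Scale.** Incidence counts participants, so k missed participants among n lower it by k/n. The planned numbers are 12 per cohort and 24 in total (Protocol 1.1, Number of Participants).

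| k missed | Cohort, k/12 | Overall, k/24 |
|---|---|---|
| 0 | 0 | 0 |
| 1 | 1/12 = 8.3 points | 1/24 = 4.2 points |
| 2 | 2/12 = 16.7 points (both in one cohort) | 2/24 = 8.3 points |

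The range of 0 to 2 is an assumption; the documents give no rate from which to estimate k.

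**The case against.** The strongest case against is that the gap is nearly empty. COVID-19 symptoms must have begun within the 5 days before treatment assignment, and COVID-19 disease history is collected at screening, so most symptoms present at entry are history and not AEs. Anticipated fluctuations of pre-existing conditions that do not worsen are also excluded from the AE definition. A symptom that exceeds expectation only after dosing becomes an AE at that point and is counted. All of this stands, and it removes much of the motivating example. It does not remove an event that is new after consent, or one already worse than expected before dosing.

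It can also be said that recording rules belong to documents outside this review: the CRF completion requirements (Protocol 10.1.7), the Analysis and Reporting Plan (SAP Appendix 2.2) and the CDISC and sponsor standards cited in the SAP. The follow-up sentence in Appendix 3 stands beside text on postmortem findings and SAE updates, and sets no rule on onset dates. This is fair, and it means that the loss is possible and not demonstrated. But nothing in the protocol or SAP says that those documents override the explicit definition in SAP 3.5.1.

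Finally, the study is single-arm, with no hypothesis, no decision rule and no formal comparison of cohorts. No formal conclusion turns on this boundary. That lowers the priority, but the incidence itself is the reported result, shown without confidence intervals (SAP 6.6.1).

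A reader might infer that such events vanish from the primary endpoint altogether. The documents do not support that, because the second component picks up those that become serious or lead to discontinuation. Nor do they support reading every such event as an 8.3-point loss, since a participant with any other TEAE is already counted.

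**Conclusion.** The point holds in a narrow form. As written, SAP 3.5.1 leaves out of the TEAE component a non-serious AE that was recorded between consent and first dose, worsens after dosing, does not lead to discontinuation and is kept on its original record. The count of SAEs and AEs leading to discontinuation is unaffected.

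The effect is probably small, because the window is short and several conditions must coincide. Its frequency cannot be estimated from the documents. Where it does occur in a participant with no other TEAE, the shift is visible in a study of this size: 8.3 points in a cohort of 12, or 4.2 points in 24. The conclusion assumes the planned numbers and that sites may update the original record. If every worsening is entered as a new AE, nothing is lost. This is a clarification worth making, not a demonstrated undercount.

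**What to change.** In SAP 3.5.1, define a TEAE as an AE that starts on or after first dose, or that started before first dose and increases in severity or becomes serious on or after it, through Day 34.

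Also state how worsening is recorded: as a new AE entry, or as a dated severity change on the existing record. The wording of the definition alone is not enough, because a single undated grade per event cannot show whether the worsening came before or after dosing.

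The cost is one sentence in the SAP, a small clarification of AE recording instructions and one derivation check. Sample size, visits and the other primary component do not change.
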